To overcome these significant gaps in prior research, we propose to demonstrate the feasibility and validity of home-based, comprehensive TeleNP. We will conduct a cross-over pilot trial to evaluate the feasibility and preliminary validity of standard, face-to-face (FF) neuropsychological assessment versus home-based video TeleNP in adults with suspected typical or atypical AD. germane to the generalizability of TeleNP to clinical settings, the trial will be embedded in the University of Colorado Hospital (UCH) Memory Disorders Clinic, which will further facilitate an appraisal of whether TeleNP assessments are appropriate for diagnostic adjudication of typical vs. atypical ADRD phenotypes. In an exploratory aim, we will utilize a mixed methods approach to assess the feasibility and acceptability of TeleNP among key stakeholders: patients, their care partners, neuropsychologists, and a psychometrist. This approach will be guided by the Unified Theory of Acceptance and Use of Technology (UTAUT) model; this theoretical framework identifies “social influence” and “facilitating conditions”, which can assess the potential influence of the home environment on user acceptance and intentions to use.¹⁶ This pilot clinical trial will delineate the feasibility of implementing TeleNP in a Neurology clinic setting and thereby prepare us for a future definitive pragmatic trial of TeleNP effectiveness across multiple clinics.

III. Preliminary Studies/Progress Report:

This is an NIH-funded R21 application with no current pilot data. There are published studies of telehealth and neuropsychology; however, the vast majority of studies using remote neuropsychological testing have been delivery of services to another health care facility, with the presence of on-site support to the patient^{8, 9, 17-20}. Although those studies emulated a “controlled” setting of a clinic, they did not address the feasibility of implementing TeleNP in a more real-world context, when the patient is at home with no staff support. **Whether due to rural-based access to care barriers, functional limitations, or COVID-19, many older patients have limited access to remote clinic offices for evaluation**, hence raising questions regarding scalability of clinic-to-remote clinic neuropsychological assessments. As such, we will appraise the feasibility and preliminary validity of TeleNP as a comprehensive neuropsychological assessment via home-based video telehealth administration.

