Face-to-face (FF) Assessment (control condition): The participant will undergo an in-person evaluation with the neuropsychologist and psychometrist at the Clinical & Translational Research Center (CTRC) or in Building 400 at CU-AMC. The standard protocol will be administered, including the interview and Core Battery. After completion of the Core Battery and submission of initial ratings, the supervising neuropsychologists may elect to have additional tests administered by the psychometrist as part of a Flexible Assessment. The Flexible Assessment will include a menu of tests that have physical/tactile stimuli (e.g., Design Fluency; Trail Making Test), all of which are excluded from the Core Battery due to lack of adaptability to video-based administration. Upon receipt of the scores from the Flexible Assessment, the neuropsychologist will complete a second form indicating any alterations to their diagnosis based on new information.

TeleNP Assessment (intervention condition): The participant will undergo a video-based TeleNP assessment using a HIPAA-compliant platform (e.g., Zoom). The participant will be at home using a study-provided tablet, and the neuropsychologist and psychometrist will administer the evaluation from either the CTRC or their CU-AMC office. During the scheduled TeleNP assessment, the standard protocol will be administered (i.e., interview and Core Battery). The psychometrist will assist with tablet collection at no direct cost to the participant (i.e., will provide a paid return box; alternatively, participant may drop off tablet if convenient to them)

Data Collection for Clinical Trial Participants:

Medical records:

--Participants will be asked to allow their past, current and future medical record information, to be placed in our RedCap database. The goal is to collect health information pertinent to cognitive functioning in older adults. Because concurrent medical conditions and treatments may impact the participants' health, it is likely that all pertinent past, current and future medical record information will be considered for inclusion in the RedCap database. This will include: symptom history and diagnostic considerations from the participants' neurology notes; laboratory results; health history (i.e., major medical problems); brain imaging results.

Demographics:

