Strategies to minimize risk: Risks to subjects are minimal and may include loss of confidentiality and psychological discomfort about discussing issues related to their neuropsychological assessment. Prior to enrollment, the study will be explained in a clear and detailed manner by the study coordinator (serving in role as coordinator and psychometrist) and investigators. All participants will be reminded at the beginning of all assessments of their right to terminate the assessment at any time. In the study consent procedure and study activities, we will clearly state that all participants can refuse to answer any questions or to review any of the study materials. Research staff will be trained to address psychological distress and will follow standard procedures for referral for mental health evaluation. We will also reassure patients that if they choose not to be in the study, it will not affect the medical care they normally receive.

We will provide neuropsychological test results from the FF condition (i.e., condition that is most congruent with standard of care) to the referring neurologist and the patient, and this information will also be placed in a research note in their UCH EMR. This will be explicitly noted in consent form and reviewed in detail with the participant. In terms of study results, there is a possibility of practice effects, particularly on memory tests and fluency tests, with serial testing. Studies suggest minimal practice effects in individuals with symptomatic Alzheimer's disease; however, given that we will provide results from the FF assessment to be used in clinical care and potentially for diagnosis, we will mitigate risk in the following way: a) use of alternate forms, where possible and b) require of at least one month between conditions. Based on these strategies, which are also used in standard of care with neuropsychological serial testing, we do not think enrollment in the study poses a significant risk of a clinically meaningful practice effect.

Strategies to manage and protect the privacy of participants and confidentiality of research data: A copy of the consent form will be given to each participant. Maintenance of subject confidentiality is a high priority for the proposed research project. Video-based TeleNP will be conducted using

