Plans for ensuring professional intervention if indicated: Participants will be given the PI's contact information for any questions or concerns about the study. Staff will be trained to identify and address psychological distress, reportable events, or threats to society including elder abuse, suicide or homicide ideation or intent, violent behavior or threats, excessive emotional outbursts, a witnessed psychotic break with visual or auditory hallucinations, verbalization of anxiety or flashbacks to past traumatic experiences, and reports of major depression (assessed in the study). For acute issues, hospital security will be called [contact]). For nonacute issues, the research team will be available in clinic to help avert crises and to schedule potential needed follow-up. If elder abuse is suspected, we will contact the patient's Colorado county law enforcement agency and county-specific adult protective services intake phone number through standard reporting mechanisms. The informed consent forms state that if elder abuse is suspected it will be reported, in accordance with State of Colorado law. A toll free crisis line will be made available to participants who may be in abusive situations ([name]), and the referring neurologist will be alerted to suspected elder abuse.

Plans for handling incidental findings: Participants will receive results from their FF research assessment. Through the process of completing the study procedures, the most likely potential incidental findings will be new or worsened physical or psychological distress, or delirium. If the intervention is stopped due to discomfort and/or the patient desires for the research staff to share information about their current needs with the patient's UCH Memory Disorders Clinic neurologist, the psychometrist will communicate this information on the patient's behalf. Of note, if information emerges during either the TeleNP or FF visit that requires immediate clinical action, or clearly would impact treatment, the neuropsychologist will immediately notify the participant and neurologist to streamline care and minimize any delays in treatment. Moreover, if any safety, psychological or other signs of distress related to potential diagnosis of AD are noted during either assessment, appropriate referrals will be coordinated by Drs. [name] and [name].

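### For TeleNP visits the protocol states urgent notice and referral but, suspected elder abuse apart, no step that sends emergency help to the participant at home

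*Combined protocol and SAP*

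**What the plan says.** Section IV.C (*Description, Risks and Justification of Procedures and Data Collection Tools*), under *Plans for ensuring professional intervention if indicated*, lists events that staff are trained to recognise and deal with. They include suicidal or homicidal thinking or intent, violence or threats, and a psychotic episode seen by staff. The action for acute issues is then given once: "For acute issues, hospital security will be called". A contact detail after these words was removed from the public copy and is not counted as a gap. The next sentence turns to less urgent matters: "For nonacute issues, the research team will be available in clinic to help avert crises". Neither sentence separates FF from TeleNP visits.

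The *TeleNP Assessment* paragraph in section IV.B sets the locations. For the participant: "The participant will be at home using a study-provided tablet". For staff: "the neuropsychologist and psychometrist will administer the evaluation from either the CTRC or their CU-AMC office". A care partner is encouraged but not required (*Additional Consenting Participants*, section IV.A).

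Four other provisions bear on the point:

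- *Plans for handling incidental findings* covers information from either type of visit that calls for immediate clinical action: "the neuropsychologist will immediately notify the participant and neurologist to streamline care".
- The same paragraph, and *Incorporation of Results into Clinical Care* in section IV.B, provide for referrals when safety concerns or distress linked to a possible AD diagnosis are noted.
- *Strategies to minimize risk* says that trained research staff "will follow standard procedures for referral for mental health evaluation". Those procedures are not reproduced.
- For suspected elder abuse, "we will contact the patient's Colorado county law enforcement agency" together with county adult protective services. A crisis line is offered to participants who may be in abusive situations.

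**The concern.** The general rule for acute issues relies on a campus resource, while in one of the two study conditions the participant is off campus. If a participant voices suicidal intent or becomes violent on video, the staff member sees it on a screen and the participant may be alone. The protocol names people to notify and routes for referral. It does not name anyone who would go to the home, unless the issue is suspected elder abuse.

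Such a disclosure is foreseeable. Each TeleNP visit opens with a 30-minute clinical interview, and the Core Battery contains a depression scale, although the battery may not be given in full every time. The protocol also treats the home setting as the feature that separates this study from earlier clinic-to-clinic work: "when the patient is at home with no staff support". That sentence is about feasibility rather than crisis response, but it describes the setting in which the acute rule would have to work.

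What is at stake is participant safety. No estimate, interval or test in the statistical analysis plan depends on it.

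**Working it through.** The plan gives no figure to reproduce here. The check sets each relevant provision against one question: would following it, as written, send help to a participant at home during a TeleNP visit?

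| Provision | Trigger | Covers TeleNP? | Stated action | Sends help to the home? |
|---|---|---|---|---|
| Acute issues (IV.C, professional intervention) | Acute issues as a class | Not stated either way | Call hospital security | Not stated |
| Nonacute issues (same paragraph) | Nonacute issues | Wording points to the clinic | Team available; follow-up scheduled | No |
| Elder abuse (same paragraph) | Suspected abuse | Yes, not tied to place | County law enforcement and protective services | Yes, for this issue only |
| Crisis line (same paragraph) | Possible abusive situation | Yes, not tied to place | Number made available | No |
| Incidental findings (IV.C) | Need for immediate clinical action | Yes, by name | Immediate notice to participant and neurologist | No |
| Referrals (IV.B and IV.C) | Safety or distress linked to possible AD diagnosis | Yes, either assessment | Referrals coordinated | No |
| Strategies to minimize risk (IV.C) | Psychological distress | Not limited by modality | Referral for mental health evaluation by procedures not reproduced | Not stated |

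The first row can be read in two ways.

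1. *The security step applies to all visits.* The text does not say that hospital security responds off campus or relays a call to responders near the participant.
2. *The security step is meant for campus only*, as the clinic wording of the following sentence suggests. The text is then silent on an acute step for home visits.

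Both readings lead to the same result: outside suspected elder abuse, no stated step sends emergency help to the participant's location.

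**Exposure.** 80 participants × 2 assessment visits = 160 visits. TeleNP share: 80 / 160 = 50%. This follows from the crossover design and is not an event rate; the documents give none. It is also not a full count of remote contacts, because consent, surveys and interviews may be remote (*Recruitment and Screening*, IV.A), including the interviews planned with 20 patients (*Outcome Measure(s)*, Aim 3).

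**Time cost of a start-of-session check.** The minutes per visit are an assumption: 1, with a range of 0.5 to 2. Each TeleNP protocol lasts 2 hours (*Protocol and Core Battery*, IV.B), so total TeleNP protocol time is 80 × 120 = 9,600 minutes.

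- At 1 minute: 80 × 1 = 80 minutes; 80 / 9,600 = 0.83%.
- At 0.5 minutes: 80 × 0.5 = 40 minutes; 40 / 9,600 = 0.42%.
- At 2 minutes: 80 × 2 = 160 minutes; 160 / 9,600 = 1.67%.

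**The case against.** The strongest reply is that the protocol does not leave TeleNP staff without an urgent step. The incidental-findings paragraph names TeleNP and requires immediate notice to the participant and neurologist. A neurologist who knows the patient could summon help, and campus staff could ask hospital security to relay a call. Staff are trained to deal with the listed events, and the standard procedures cited under *Strategies to minimize risk* may contain an emergency route. The protocol expects most care partners to live with the participant and encourages them to help set up the home session, so many participants will not be alone. The exclusion criteria remove moderate to severe dementia, active delirium and major psychiatric disorder, and the protocol calls the risks minimal.

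Much of this stands. A reader might infer that the protocol has no emergency step of any kind for TeleNP. The documents do not support that, because the immediate-notice rule is an urgent step that covers TeleNP by name. A reader might also infer that the protocol tells staff to send hospital security to a private home, or that the study team has no emergency plan. The first is not supported because the security sentence may be meant for campus only. The second is not supported because operating procedures and the consent form are outside the copy reviewed.

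The objection does not remove the narrower gap. Notice and referral tell someone about the problem; neither is stated to bring a responder to the participant. Any relay by security or the neurologist is conjecture. A care partner is expected in many cases but guaranteed in none.

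**Conclusion.** The point holds in limited form. For acute issues as a class, calling hospital security is the only stated action, and it is not split by modality. For TeleNP visits the protocol adds immediate notice and referral. It states no step that sends emergency help to the participant's location, except the contact with law enforcement and protective services for suspected elder abuse.

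The exposure is half of the planned assessment visits, plus other remote contacts. The risk per visit cannot be estimated from the documents and is probably low given the exclusions. No analysis is affected. This is a low-severity safety improvement, worth making because it is cheap and changes what staff would do.

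The conclusion rests on the public protocol text alone. It would fall if the standard procedures cited in section IV.C, or another operating procedure, already direct staff to emergency services near the participant. In that case a cross-reference would be enough.

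**What to change.** In *Plans for ensuring professional intervention if indicated*:

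- Limit the hospital-security step to visits held on campus.
- State that, for acute issues at a TeleNP visit or any other remote contact, staff will call emergency services local to the participant, and the care partner or an emergency contact if available, alongside the existing immediate notice to the neurologist.
- Add that each TeleNP session starts by confirming the participant's location, a call-back number and who is present.

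The third item can build on the pre-visit call and on the address and contact details, which the protocol already collects for scheduling. Confirming location on the day matters because the loaned tablet is 4G and need not be at the address on file. A call-back number helps if the video connection drops.

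The cost is about 80 staff minutes over the trial (40 to 160 under the assumed range), or roughly 0.8% of TeleNP protocol time (0.4% to 1.7%). To this add brief staff training, a minor protocol amendment with ethics-board review, and possibly one consent sentence saying that emergency services may be called. The consent form was not in the copy reviewed and may already say so. The amendment needs no extra visits and leaves the statistical analysis unchanged.

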The overarching goal of this proposal is to a) assess the feasibility and preliminary validity of **home-based delivery of TeleNP** to patients with suspected AD, referred for cognitive assessments in a Neurology Clinic; and b) elucidate whether TeleNP is equivalent to face-to-face evaluation (FF) for diagnostic adjudication of atypical versus typical AD. To accomplish these goals, we will conduct a **pilot clinical trial** of two testing modalities, TeleNP versus FF, for delivery of neuropsychological evaluations. Neurologist-referred patients with typical (i.e., memory-predominant; n=40) and atypical (i.e., complex and/or non-memory predominant; n=40) presentations of *possible* AD will be enrolled in the study. Care partners of participants will also be consented to the study and included in stakeholder surveys/interviews. Using a cross-over design, all participants will undergo evaluations (clinical interview + Core Battery of cognitive tests) in both modalities, approximately 4-6 weeks apart to account for potential practice effects. Although all participants will be referred due to suspected AD, the neuropsychologist will be blinded to the specific diagnosis (i.e. typical versus atypical) from the neurologist. The Core Battery will include measures of memory, executive, visuospatial, and language functions. To further minimize practice effects, alternate assessment forms will be implemented and order of test forms will be counterbalanced. Some tests are not readily adaptable to video-based delivery due to tactile/physical stimuli; as such, we will assess whether a Flexible Assessment (i.e., option to include additional tests, after completion of Core Battery) in the FF modality alters diagnostic conclusions. Finally, in an exploratory aim, we will identify stakeholder perspectives of TeleNP that inform pragmatic implementation of remote neuropsychological evaluations. Our Aims are:

Aim 1: Determine the validity of home-based video administration of neuropsychological tests (TeleNP) for assessing AD. 1a: Are cognitive test results equivalent across TeleNP and FF conditions in patients with suspected AD? 1b. Is this equivalence consistent across referral diagnoses (i.e., Typical vs. Atypical AD)? *This Aim will test the validity of cognitive measures assessed with TeleNP and determine whether the validity of TeleNP differs based on referral diagnosis.*

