HIPAA privacy notification language will be incorporated into the informed consent document and will be signed by all participants prior to any procedures being carried out. Informed consent language will include key facts about the study, the study events, timeline, the study participant's role in the study, potential risks and benefits and highlight the fact that participation is completely voluntary and will be signed by all study participants. The informed consent/HIPAA form will specify that the database will receive and store all research data. Information regarding the purpose and procedures for this project will be given in both oral and written form. All study participants will be consented in privacy and will be given as much time as they need to read, discuss and ask questions about study events and their respective roles and participation in the study. They will be reassured that the same ethical and legal codes that govern medical practice

[figure not shown]
also apply to clinical research and they will be given the opportunity to ask questions and receive information regarding the goals and details of this study. If the Principal Investigator or Co-Investigators do not initially participate in the discussion, they will be available to answer questions prior to obtaining written informed consent/authorization.

Subjects may withdraw participation in the study at any time by calling, writing, or emailing the Principal Investigator or study coordinator. Subjects will be unable to withdraw data that has already been analyzed, presented, or published.

B. Study Design and Research Methods

Randomization, Intervention and Neuropsychological Assessment Methods

Study participants will undergo both modalities (FF; TeleNP), conducted 4-6 weeks apart (allowing for maximum of 90 days). Order of modality will be randomized at baseline using a computerized process through REDCap, developed by [name]. Similarly, assignment of supervising neuropsychologist will be randomized and counterbalanced across testing conditions. Our goal of using two neuropsychologists is to minimize bias; specifically, use of the same neuropsychologist for the same patient across both modalities would likely influence their interview approach and diagnostic adjudication due to recollection of the prior assessment.

Abbreviations and Terminology:

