Mild practice effects may be observed regardless of order of administration, which is commonly noted in standard of care with serial testing; however, given that results will be provided from the FF condition (i.e., the condition most comparable to standard of care), there is a small possibility that this may result in a slight overestimation of participant's cognitive abilities for those who undergo the FF condition second. See mitigation of risks below, as we will use validated mitigation strategies used in standard of care for serial testing.

The neuropsychological tests selected for this research study are identical to measures used in standard of care, with the FF condition being comprehensive and comparable to SOC. Standard of care for neuropsychology is not set in stone, meaning that the duration of the assessment is often provider-dependent. For reference, the tests and the length of the assessment are comparable to the standard neuropsychology battery – both in terms of content and duration – that the PI ([name]) uses in clinic for the same patient population. All tests selected were chosen based on their standard use in clinic, their ability to carefully characterize cognitive strengths and weaknesses, and their utility in assisting with differential diagnosis. Thus, we do not think that that the participant would receive a less comprehensive assessment in the research study than they would receive as part of standard of care.

Risks to privacy and/or confidentiality: Participants face a potential risk to privacy or loss of confidentiality related to private identifiable information and the research materials (test results) that they may provide as a study participant.

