To improve reach to participants who have limited access to technology and conduct TeleNP using a standardized technology platform, we will provide a 4G tablet to all participants via a research lending library. Participants will be encouraged to bring a care partner, if available, with them to visits (i.e., FF and TeleNP); however, consistent with standard clinical practice, the availability of a care partner will not be a requirement.

E. Potential Scientific Problems:

Practice Effects: Repeated administration of cognitive tests is sometimes associated with practice effects, which may impact interpretation of results. Practice effects have been shown to be lower in symptomatic (MCI, dementia) patients relative to asymptomatic adults³⁴; with respect to individual domains, verbal memory tests and verbally-mediated executive function measures appear to be most vulnerable to practice effects, with visuospatial measures less impacted. In estimating practice effects over a 3- to 6-month period, maximum effect sizes have ranged from 0.10 to 0.15 based on drug trials, which are quite small.³⁴ Our proposed period (4-6 weeks) occurs over a shorter duration. Based on recommendations for clinical trials³⁴, we will use alternate forms, where available (i.e., memory tests; fluency measures; attention/working memory). Of note, we will provide feedback to the patient and referring neurologist based on the FF assessment. In cases where the participant undergoes the FF assessment *after* the TeleNP condition, it is possible that aforementioned practice effects, albeit very small, may influence the mean scores obtained for each cognitive domain. Serial testing is common in standard neuropsychological practice, thus we will use validated approaches (i.e., alternate forms) for tests that are most vulnerable to this effect.

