F. Statistical Analysis Plan:

For **Aim 1**, we will adopt an equivalence testing framework. The null hypothesis is that there is an average difference of at least .5 SD units in the difference in the z-scores, where .5 SD defines a potentially clinically meaningful difference. The alternative hypothesis is that the mean of the

difference in the z-scores is zero. This is the reverse of standard statistical testing. We elected a .5 SD margin as an initial threshold for a clinically meaningful difference; the reason for this decision is that once an individual reaches a level deemed to be clinically significant impairment (e.g., mild impairment = -1.5 SD; moderate impairment =-2.0 SD), a change in .5 SD equates to a categorical difference in their overall severity rating. To conduct our equivalence test, we will compute the difference in the z-score between the FF and TeleNP conditions and compute the mean difference and a 90% confidence interval based on a t-test. This results in an equivalence test with an alpha=0.05. If the entirety of bounds of the 90% confidence interval are between (-.5SD, .5SD), then the two assessments will be considered equivalent. We will repeat this computation stratified by referring diagnosis (typical vs. atypical), and also by sex or race/ethnicity (white vs. non-White).

For **Aim 2**, we will compute a 3x3 table with the rows as TeleNP diagnosis and the columns as FF diagnosis to summarize the results. To assess the equivalence of TeleNP and FF for each condition we will create 3, 2x2 tables. For example, when assessing for differences in typical AD we will collapse over atypical AD and Not AD. Following prior work³⁵, we will compute the difference proportion of typical AD for the TeleNP and FF setting and construct a 90% confidence interval. A difference of proportions greater than 5% will be considered a clinically meaningful difference. If the 90% confidence interval is between (-5%,5%), then the two modalities will be considered equivalent. We will repeat this process for the two other neuropsychologist-determined categories (atypical AD, Not AD). We will conduct the same analyses, stratified by severity. We will assess whether the neuropsychologists' diagnosis is equivalent to the Flexible Assessment by repeating the above analysis using the Flexible vs FF diagnosis (i.e., diagnosis reported prior to initiating Flexible Assessment).

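### The Aim 1 equivalence interval leaves out the randomised visit order; adding it overall and in the two referral-diagnosis strata is a cheap, minor improvement

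*Combined protocol and SAP*

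**What the plan says.** Section IV.B (Study Design and Research Methods) describes two visits per patient, one in each modality: "Order of modality will be randomized at baseline using a computerized process through REDCap". It does not state an allocation ratio, blocking, or stratification by referral diagnosis.

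The protocol discusses practice effects in three places.
- Description of Risks accepts a small possibility of slightly overestimating "cognitive abilities for those who undergo the FF condition second".
- Section IV.E (Practice Effects) gives a size: "maximum effect sizes have ranged from 0.10 to 0.15 based on drug trials". It adds that, when FF follows TeleNP, "it is possible that aforementioned practice effects, albeit very small, may influence the mean scores obtained for each cognitive domain".
- The remedies are in the design. Specific Aims says that "alternate assessment forms will be implemented and order of test forms will be counterbalanced", and Strategies to minimize risk lists "require of at least one month between conditions". Section IV.E limits alternate forms to tests for which they exist.

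The SAP (section IV.F, Aim 1) will "compute the mean difference and a 90% confidence interval based on a t-test" and declare equivalence if the interval lies within ±0.5 SD. It continues: "We will repeat this computation stratified by referring diagnosis (typical vs. atypical), and also by sex or race/ethnicity (white vs. non-White". No section puts visit order into this analysis. The exploratory look at provider effects in section IV.E concerns a different factor.

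**The concern.** With a practice gain, a patient seen FF first has a difference pushed towards TeleNP, and a patient seen TeleNP first has one pushed towards FF. A one-sample interval treats that predictable spread as noise. If the two orders are completed in unequal numbers, the pushes do not cancel and the centre of the interval moves. The domain means that the protocol says practice may influence are the quantities that Aim 1 tests, and several Core Battery tests are listed without alternate forms (for example Color Word Inhibition and the short Judgment of Line Orientation). Design measures therefore reduce practice but are not shown to remove it. What is at stake is a little precision and, near the margin, an equivalence call that leans one way because of the split that happened to occur.

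**Working it through.** **Inputs from the documents.** 90% interval and ±0.5 SD margin (SAP, Aim 1); 80 patients, 40 per referral-diagnosis stratum (Specific Aims; section IV.A); practice p = 0.10-0.15 (section IV.E).

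**Assumptions.** p and the margin are in z units; the SD of within-patient differences is s = 0.4-0.7; a 25/15 completed split illustrates imbalance.

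**1. The plan's own figure.** (1 - 0.90)/2 = 0.05 per one-sided test, which matches the stated alpha.

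**2. Model.** With true modality difference δ, the mean difference is δ - p for FF first (n1 patients) and δ + p for TeleNP first (n2 patients). The overall mean therefore estimates δ + p(n2 - n1)/n. At 25/15 the shift is 0.10 × 10/40 = 0.025 to 0.15 × 10/40 = 0.0375, and at equal counts it is zero.

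**3. Half-widths.**
- Planned: t(.95, n-1) × √{[s² + 4p²n1n2/(n(n-1))]/n}
- Order-adjusted: t(.95, n-2) × (s/2) × √(1/n1 + 1/n2)

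Example at 40/40, s = 0.5, p = 0.15. Planned: 1.6644 × √[(0.25 + 0.0228)/80] = 0.0972. Adjusted: 1.6646 × 0.25 × √0.05 = 0.0931.

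| 40/40 | planned, p 0.10 | planned, p 0.15 | adjusted | planned wider by |
|---|---|---|---|---|
| s 0.4 | 0.0768 | 0.0796 | 0.0744 | 3-7% |
| s 0.5 | 0.0949 | 0.0972 | 0.0931 | 2-4% |
| s 0.7 | 0.1316 | 0.1333 | 0.1303 | 1-2% |

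**4. Stratum of 40 at 25/15, s = 0.5.** Planned: 0.1332 (p = 0), 0.1357 (p = 0.10), 0.1388 (p = 0.15). Adjusted: 1.6860 × 0.25 × √(1/25 + 1/15) = 0.1377. The adjusted interval is 3.3% wider at p = 0, 1.4% wider at 0.10 and 0.9% narrower at 0.15. Setting the two formulas equal, it is narrower only if p exceeds 0.106 (s 0.4), 0.133 (s 0.5) or 0.186 (s 0.7).

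**5. Effect on the decision (simulated, n = 40).**
- *Averaged over simple randomisation, true difference at the margin:* the planned test falsely declares equivalence with probability 0.050. With balanced orders it is slightly conservative (0.042-0.048 at p = 0.15, in runs at n = 40 and n = 80).
- *True difference 0, split 25/15:* equivalence is declared with probability 1.00 (s 0.4-0.5) or 0.99 (s 0.7), with or without the order term.
- *Given a 25/15 split, s = 0.5, true difference 0.30, p = 0.15:* planned 0.89 or 0.62 depending on which order is larger; adjusted 0.78.
- *Given a 25/15 split, s = 0.5, true difference exactly at the margin:* planned 0.086-0.107 when the shift is towards zero and 0.014-0.024 when it is away; adjusted about 0.05.
- *Chance of the lenient split:* if order is simply randomised, 25/15 or worse in that direction has probability P(Bin(40, 0.5) ≤ 15) = 0.077 per stratum.
- *Averaged over simple randomisation, true difference 0.30, s = 0.5:*

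| p | planned | adjusted |
|---|---|---|
| 0 | 0.799 | 0.789 |
| 0.05 | 0.797 | 0.791 |
| 0.10 | 0.788 | 0.791 |
| 0.15 | 0.768 | 0.789 |

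**The case against.** The strongest reply is that nothing in the plan is wrong. Randomised order makes the planned interval unbiased and keeps its level, and this is a self-described pilot. The practice figure used here is the protocol's maximum, and alternate forms and spacing should lower it. The gain is also small in absolute terms: at 40/40 and SD 0.4 it is 0.002-0.005 SD against a margin of 0.5 SD. In an unbalanced stratum the order term can cost precision. At 25/15 with SD 0.7 the adjusted interval is wider across the whole 0.10-0.15 range.

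All of this stands, and it sets the weight of the point. It does not remove the point, because once the visits are done the split is known and the planned interval ignores it. The practice figure is also not a proven ceiling here: it comes from drug trials over 3-6 months, while visits are 4-6 weeks apart and alternate forms do not cover every test.

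A reader might infer from the conditional figures of 0.086-0.107 that the Aim 1 test has an inflated type I error. The documents do not support that. Those figures need a true difference exactly at the margin, practice of 0.10-0.15 and an uneven split in one direction. The opposite split makes the test too strict, and the average is 0.050.

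**Conclusion.** The point holds as a minor improvement, for the overall analysis and the two strata of 40. The order term is absent, the variable is already recorded, and the protocol itself gives the reason to use it. Under the stated assumptions the benefit is a 1-7% narrower interval at 40/40 and removal of a chance shift of 0.025-0.038 SD at 25/15. The average change in power at a true difference of 0.30 (n = 40, SD 0.5) is small and can have either sign, from about -1 point with no practice to about +2 points at p = 0.15. The conclusion is unaffected when the true difference is near zero.

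The absence of the order term can be read directly from the SAP. The sizes depend on an assumed SD of differences and on reading the practice figure in z units; the probability of an uneven split also assumes simple randomisation. A reader might also infer that adjustment is always more precise, or that it should be carried into every subgroup. Neither follows: the break-even values of p exceed 0.10 at 25/15, and the sex and race/ethnicity subgroups have no planned size.

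**What to change.** In section IV.F, Aim 1, add for each domain, overall and in the two referral-diagnosis strata:

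> The modality effect is the average of the mean FF-TeleNP differences in the FF-first and TeleNP-first orders (difference regressed on order coded ±1/2; intercept, n-2 degrees of freedom). Equivalence is concluded if its 90% CI lies within (-.5, .5). Completed counts by order are reported, with the unadjusted interval as a sensitivity analysis.

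For all sex and race/ethnicity subgroups, keep the planned unadjusted interval as the single rule, with no choice of estimator, and report counts by order. A separate order term could be very costly there. In an assumed subgroup of 8 split 7/1 (SD 0.5) its half-width is 0.519, against 0.338 unadjusted (p = 0.10), and at 8/0 it cannot be estimated.

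The cost is one degree of freedom and some loss of precision when orders are uneven and practice is small (about 3% at 25/15 with no practice). No new data or visits are needed.
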